9. ADVERSE EVENTS AND RISKS

9.1 Adverse Event Definitions

Adverse Event (AE)

Adverse event data is collected as part of the study design and will form part of the secondary outcomes of the study. Conditions that are present at screening and do not deteriorate will not be considered adverse events. These outcomes will be routinely reported via standard hospital internal reporting methods/risk management processes. If any of the attending clinicians suspect an adverse event that is related to the study design, such an adverse event will be immediately reported to the Chief Investigator and Townsville HHS HREC.

For the purposes of this study the site investigator is responsible for recording all AEs, regardless of their relationship to study intervention. Conditions that are present at screening and do not deteriorate will not be considered AEs.

Serious adverse event (SAE)

SAEs for this study are defined as:

- Hypoxaemia leading to cardiac massage which the clinician believes is related to one of the study interventions
- Cardiac arrest: Loss of spontaneous cardiac output
- Mortality (all events will be reported)
- OR any life-threatening medical event or reaction which the clinician believes may be study related

Adverse event (AE)

AEs are defined as but limited to the following:

- Severe hypoxaemia with saturations <80% for longer than 1 minute
- Pneumothorax
- Unexpected need for endotracheal tube placement
- Bradycardia: bradycardia not requiring treatment; bradycardia of <60/min [27, 28]

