9.4 Eliciting adverse event information

AEs will be documented from physical examination findings, clinically significant lab results or other documents that are relevant to patient safety.

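### The AE list in section 9.1 is closed as worded, against sections 9.3 and 9.4, and its bradycardia item leaves out treated bradycardia at 60/min or above

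*Protocol*

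**What the plan says.** Section 9.1 sets out SAEs and AEs separately. The AE list opens with "AEs are defined as but limited to the following" and has four items: "Severe hypoxaemia with saturations <80% for longer than 1 minute", pneumothorax, unexpected endotracheal intubation, and "Bradycardia: bradycardia not requiring treatment; bradycardia of <60/min".

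The SAE list covers cardiac massage after hypoxaemia if the clinician thinks it related, "Cardiac arrest: Loss of spontaneous cardiac output", every death, and "OR any life-threatening medical event or reaction which the clinician believes may be study related".

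The same section says that "the site investigator is responsible for recording all AEs, regardless of their relationship to study intervention", and that AE data contribute to the secondary outcomes. Section 9.3 asks, for each AE, for a description, a severity grade starting at mild, and the treatment or other action taken. Section 9.4 adds that "AEs will be documented from physical examination findings, clinically significant lab results or other documents that are relevant to patient safety". Section 3.6, item 7, names a reduction in adverse effects as a health service outcome.

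**The concern.** There are two separate faults in the definition.

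First, the lead-in restricts AEs to four items, while the next sections describe a collection process that makes sense only if other events can be AEs. The duty to record all AEs does not settle this, because AE is the very term that the list restricts.

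Second, the bradycardia item uses the absence of treatment as a condition for being counted. Within some range of heart rates, the event that was left alone is an AE and the same event that needed treatment is not. A safety definition would normally do the opposite, or ignore treatment altogether.

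At stake is the safety comparison between control and intervention periods. The bundle is meant to keep more children in local hospitals, and section 9.5 names delayed transfer as a potential risk, so harms short of death or arrest need to be countable. Section 7.1 has data taken from records at 14 hospitals and applies the same collection to historical admissions. An ambiguous item can be abstracted differently by site and by period. An analysis plan could choose how to tabulate AEs, but it cannot recover events that sites did not enter because the definition excluded them.

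**Working it through.** No arithmetic applies: the plan gives no AE rate, bradycardia count or treatment share. The check sorts types of event by the wording of section 9.1.

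The semicolon in the bradycardia item can be read in two ways:
- Alternatives: an event counts if it was untreated, or if the rate was below 60/min.
- Joint: an event counts only if it was untreated and the rate was below 60/min.

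| Event | AE, clauses as alternatives | AE, clauses joint |
|---|---|---|
| Bradycardia below 60/min, untreated | yes | yes |
| Bradycardia below 60/min, treated | yes | no |
| Bradycardia at 60/min or above, untreated | yes | no |
| Bradycardia at 60/min or above, treated | no | no |
| Unlisted harm, not life-threatening | no | no |

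The table shows three things:
1. Treated bradycardia at 60/min or above is not listed on either reading.
2. On each reading there is a range where the untreated event counts and the treated one does not: at 60/min or above if the clauses are alternatives, below 60/min if they are joint.
3. An unlisted harm that is not life-threatening is excluded whichever way the bradycardia item is read, because that exclusion comes from the lead-in.

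The SAE list catches some of what is left out. A treated bradycardia becomes an SAE if it amounts to cardiac arrest, leads to death, accompanies hypoxaemia with cardiac massage thought related, or is life-threatening and thought possibly study related. Otherwise it is neither AE nor SAE on the literal wording.

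Set against the neighbouring sections:
- Section 9.4 names clinically significant laboratory results as a source of AEs, but none of the four listed items is defined by a laboratory result.
- Section 9.3 asks for a description of each AE and a grade from mild upward, which suggests a wider set than four named events.
- Section 9.3 records treatment as an attribute of an AE. In the bradycardia item of section 9.1, treatment decides whether there is an AE at all.

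Section 9.1 therefore disagrees with sections 9.3 and 9.4 on both points, and no other section corrects it.

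**The case against.** The strongest reply is that the lead-in has simply lost the word *not*. The phrase reads awkwardly as printed, and sections 9.3 and 9.4 and the broad recording duty all point to an open list. This is plausible. On that reading, unlisted harms are back in, and a treated bradycardia at 60/min or above could be entered as a further AE. But nothing in the protocol makes the correction, and opening the list would not mend the bradycardia item, which would still name the untreated event and leave its two clauses unreconciled. The item cites two references that are not at hand and might explain it; the text itself does not.

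A reader might go further and infer that unlisted harm is counted nowhere. The documents do not support that. Deaths and cardiac arrests are SAEs with no condition of relatedness, and life-threatening events thought possibly study related are SAEs too. Section 9.1 also refers to routine hospital reporting and to immediate notification of suspected study-related events, and section 8.3 obtains adverse reactions by linkage for the costing work.

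A reader might also infer that training will lower the AE count by a definite amount because staff will treat bradycardia earlier. A definition that depends on treatment could shift if practice shifted, but the protocol gives no bradycardia or treatment frequencies, and its outlines of the bundle and training (sections 6.1 and 6.2.2) do not mention treating bradycardia. No size can be put on this.

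Finally, section 3.5 does not list AEs and section 8.2 gives no AE model. That is fair as far as analysis goes and may be left to an analysis plan. The definition of what sites record is fixed here.

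**Conclusion.** The point holds as a contradiction within section 9 and a faulty item in an operative safety definition. As worded, two groups fall outside the AE definition unless they meet an SAE criterion: unlisted harms that are not life-threatening, and bradycardia at 60/min or above that required treatment. If the bradycardia clauses are joint, treated bradycardia below 60/min is also outside the AE list.

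The first group depends on taking the lead-in as printed, and it disappears if that is a slip and is corrected. The fault in the bradycardia item remains either way. The number of events affected is unknown and no distortion of a particular analysis has been shown. The correction is still worth making, because AE data feed the secondary outcomes and a named service outcome, and the change is a small one of wording.

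**What to change.** Two changes in section 9.1:
1. Reword the lead-in so that AEs include, but are not limited to, the listed items. This brings it into line with sections 9.3 and 9.4.
2. Reword the bradycardia item so that whether treatment was given is not a condition for counting the event. The sponsor must reconcile the two existing clauses and state how they relate; no heart-rate threshold is proposed here.

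No new form field is needed. Section 9.3 already has the treatment or action taken recorded for each AE, so treated and untreated bradycardia can both be counted and shown separately.

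The cost is a protocol wording amendment and a somewhat higher reported AE count. The revised wording should be applied alike to control, intervention and historical records, so that the wider definition does not itself create a difference between periods.

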9.2 Reporting of SAEs

All SAE data will be recorded on a SAE form on the CRF and submitted to the Townsville HHS HREC within 24-72hrs, in accordance with the safety reporting policy of HREC. Information reported will include: patient initials and study number, nature of the event, start and end time of the event, investigators opinion of relationship between implementation of the respiratory care bundle and the event (unrelated, possibly, probably or definitely related). Notification to the Townsville HHS HREC and their response may require amendment/s to the respiratory care bundle. If this occurs the necessary changes will be made.

9.3 Assessment and documentation of adverse events

The description of each AE on the CRF will include all of the following:

- Description of the AE
- Onset date, duration, date of resolution
- Severity (mild, moderate or severe)
- Seriousness
- Treatment/Management/Action taken
- Outcome (recovery, death, continuing, worsening)
- Likelihood of relationship of AE to the study treatment (Unrelated, Possible, Probable, Definite).

Changes in the severity of an AE will be recorded on the CRF.

AEs characterised as intermittent will be documented for each episode.

All AEs will be followed to adequate resolution or stabilisation, where possible.

9.4 Eliciting adverse event information

AEs will be documented from physical examination findings, clinically significant lab results or other documents that are relevant to patient safety.

9.5 Risk/benefit analysis

Individual patient care will be driven by standard practice before and after implementation of the respiratory bundle. An independent data safety monitoring board (DSMB) will be tasked to monitor study progression and assess trajectory of study outcome.

Potential risks.

This study is performed in a health care setting with a relatively high staff turnover. This may lead to decreased adherence to the respiratory care bundle. Mitigation: the education will be part of the required mandatory education in each hospital.

A delay in the transfer of patients who definitively require high level of care. Mitigation: the bundle sets robust boundaries and thresholds of when escalation must occur and hence this is unlikely to occur. Patient care will occur within the standard clinical treatment framework.

Potential benefits.

Reduction of unnecessary transfers to higher level of care. Increased clinical staff knowledge, confidence and skillset caring for children less than 5 years with acute respiratory failure. Increased clinical staff and consumer satisfaction.

10. DATA SECURITY

10.1 Data Storage

Data will be stored and locked by the investigating site in a locked cupboard in a secured location. Electronic data will be securely stored on the RedCAP databased, hosted by

Griffith University, Queensland. Following analysis, data will be transferred to a password protected computer file and stored on the secured and backed up drive at Griffith University, Brisbane.

10.2 Record Retention

As required by the Queensland State Archivist, and in keeping with the QH Retention and Disposal Schedule 2DAN546 v3 (Clinical research records for minors – Section 2659), all study information and documentation will be securely stored until the patient reaches one of the following retention age periods, before being securely destroyed. This also complies with the Australian Code for the Responsible Conduct of Research Section 2.1.1

- Retain until patient/client attains 18 years of age AND
- Retain for 15 years from completion of clinical research/trial or after date of publication or termination of the study AND
- 10 years after last patient/client service provision or legal action, whichever is the later.

11. STUDY OVERSIGHT

Oversight and Governance.

The trial will be overseen by a **Trial Steering Committee (TSC)**, the membership of which will include: the CIA, and at least 2 further CIs. The role of the TSC will be to: monitor and supervise progress of the trial; review at regular intervals relevant information from other sources.

The **Trial Management Team** consists of the chief investigator, the project manager, and the lead educator.

Site trial management will be coordinated within each Hospital and Health Service (HHS) by a Site Trial Management Team consisting of the HHS PI and an HHS research nurse. The site PI will be responsible for local oversight of the study including: monitoring safety; ensuring that the study is conducted according to the protocol; and ensuring data integrity. The site PI will review the data for safety concerns and data trends at regular intervals and will promptly report to the Townsville HHS HREC and the central coordinating team any significant protocol deviation or any other significant event or problem that arises during the conduct of the study.

Quality Control and Quality Assurance

To standardise the collection of data by local research nurses, training of the research nurse will be undertaken by the lead educator; the research nurse will train the remaining local clinical team in particular the senior medical staff.

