In the first year of this project the existing training capacity of each hospital will be assessed, and gaps identified. The training will occur on two levels. The first level is provided by the local research nurse allocated to each site. The local research nurse will be provided with their training by the lead investigator and study coordinator to ensure consistency. This will be a 'Train the Trainer' model. In collaboration with the local nurse educator the local research nurse (now fully educated and trained) will apply the relevant training material and continue education throughout the project. The second level of training will be provided by SToRK (Simulation Training on Resuscitation for Kids), using resources already available and new training material. We will use online training material using the QHEPS platform, which includes training videos and access to the current Queensland Health guidelines via Queensland Paediatric Emergency Guidelines (QPEC). The training package will be adapted to the local context for maximum impact and sustainability.

6.2.3 Development Process of an Acute Respiratory Care Bundle for the local context in rural and remote hospitals:

A QLD Health led working group which will include members from the Remote PARIS expert panel will meet for round table discussions for the purpose of reaching consensus on a Respiratory Care Bundle for the safe management of patients less than five years of age (4yrs + 364 days) presenting with ARF at any of the participating hospitals. The working group participants will be provided with verbal and written information about this research project and invited to participate in the working group.

Working Group members will be drawn from key local stakeholders as well as those involved in retrieval, and clinical governance. These will include:

- Medical Superintendents/Director of Paediatrics and/or Emergency Department of each Hospital and Health Service
- RFDS and Retrieval Services Queensland
- SToRK
- Cairns and Townsville Base Hospital: Emergency, Paediatrics, Intensive Care Unit
- Children's Critical Care and Emergency Research Group, Gold Coast University Hospital, Brisbane (earlier PARIS RCT clinical research leaders)
- Local nurse/medical representation

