Data will be collected in an online REDCap database. In each site the emergency admissions will be screened for children 0-4 years of age presenting with respiratory symptoms. Data on the baseline demographics, physiology at presentation and initial medical management will be captured. Length of hospital stay, length of oxygen therapy, type of oxygen therapy, and amount of oxygen resources will be captured. Further information will be captured on methods of oxygen therapy. Adverse events will be recorded. For children who required transfer to high level of care, vital signs and clinical diagnosis and medical therapy provided at time of decision to transfer will be collected. Data on respiratory support during transfer, mode and length of transport and data on treatment in accepting hospital and length of hospital stay will be collected. Adherence to the respiratory care bundle will be measured by the number of frequency of deviations from the protocol.

Twelve parents per hospital using a face-to-face structured interview will complete a paediatric proxy health related quality of life measurer (PedsQL).

Historical Control. Admissions (HBCIS) to the participating hospitals in year 2016-2022 will be screened using the same screening log as in the main protocol (Year 2020-2022 will be separately analysed due to impact of COVID-19 pandemic) and the same data collection as above used.

Time Points for Data Collection. All physiological (heart and respiratory rate, temperature) and blood parameters (arterial gases) that are captured in the medical records during the hospital admission and where relevant during the transfer for higher level of care. If admitted to a tertiary hospital, data on respiratory support provided will be captured.

Specific data

The specific data set mirrors in its basic form the data captured in our previous 3 large RCT's using nasal high-flow in children with ARF or bronchiolitis. Additional data on out-of-pocket expenses and lost income will be recorded.

Background data:

Background data collection will be collected as per the CRF. Below outlines some of the specifics which continue the same data collection of the 3 large RCT's.

Demographics:

- Age (on admission)
- Gender
- Weight (on admission)
- Ethnicity
- Diagnosis at admission
- History and risk factors
 - Prematurity (<37 weeks at birth)
 - Previous neonatal respiratory support post delivery
 - Previous Intensive Care admission post delivery

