8. STATISTICAL METHOD

8.1. Sample Size

Pre COVID-19, the participating 14 hospitals in Far North QLD have admitted over 4 years (2016-2019) a total of 2532 children with ARF. The transfer rate in these hospitals was during this period 25%. With the implemented intervention of the full study in 14 hospitals, we aim to achieve a reduction in transfers from 25% under the existing respiratory care pathways to 12.5% under the intervention condition (for all children with ARF aged 0-4 years). Our sample size of minimal eligible participants of 90 patients per hospital (1,260 patients in total) achieves over 85% power to detect this difference in transfer rates assuming an intracluster correlation coefficient of 0.1 and using a two-sided test at the 5% level of significance with the Stata function “stepped wedge”. [15, 16] Our calculation under a stepped wedge design assumes a sequential rollout schedule of the intervention that has 4 steps, with 3 or 4 hospitals randomised at each step and an average of 18 patients per hospital per time point within a 6-month interval (i.e. a total of 90 patients per hospital including baseline recruitment). The total trial duration will be 31 months including a 1-month transition period for each hospital.

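### One unblinded local role both trains staff in the bundle and collects the trial data, with no fixed case-finding rule, so the primary denominator could shift at crossover

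*Protocol*

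**What the plan says.** **Who trains.** Section 6.2.2 describes two levels of bundle training: "The first level is provided by the local research nurse allocated to each site", and the second comes from the simulation team. The nurse also continues the education for the rest of the project. Section 11 adds that "the research nurse will train the remaining local clinical team in particular the senior medical staff".

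**Who collects.** The same sentence of section 11 opens with "To standardise the collection of data by local research nurses, training of the research nurse will be undertaken by the lead educator". Section 4.2.2 makes the local research team responsible for collecting, entering and validating data.

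**Who screens.** Section 7.1 says only that "In each site the emergency admissions will be screened for children 0-4 years of age presenting with respiratory symptoms". No role is named. Patients are located through an EDIS export; historical admissions come from HBCIS, using the same screening log as the main study.

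**Who counts as a case.** Section 3.8.1 takes admitted children aged 0-4 years with acute respiratory symptoms, whether or not they need oxygen or show increased work of breathing or wheeze. Section 3.8.3 has no exclusions and intends to capture every episode.

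**Blinding.** The only statement (5.1) keeps the study investigators blind to outcome data until database lock.

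**Outcome and model.** The primary outcome (3.4) is a proportion transferred. Section 8.2 adjusts for hospital, rollout time and possibly district.

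**The concern.** Transfer is a recorded event and leaves an assessor little room. The denominator is softer. A child with mild symptoms and no oxygen requirement can meet the definition or not, depending on what was charted and how the chart is read. The person collecting the data knows whether the hospital has crossed over and has helped to deliver the bundle there.

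The bundle also acts on the material from which eligibility is read. It calls for vital signs, early-warning scoring and work-of-breathing assessment (6.1.1, 6.1.2), and recognition of bronchiolitis or ARF is one of the knowledge domains measured in staff (7.2). Better recognition and charting after training could bring more mild children into the count. Such children add to the denominator and little to the numerator, so the transfer proportion falls with no change in transfers.

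A shift of this kind starts when each hospital crosses over. In the section 8.2 model it coincides with the intervention indicator, so neither the hospital effect nor the rollout-time adjustment can separate it from the bundle's effect. The direction described favours the bundle.

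**Working it through.** **1. Inputs (section 8.1 unless stated).** Planned effect: "a reduction in transfers from 25% under the existing respiratory care pathways to 12.5% under the intervention condition". Power: the design "achieves over 85% power to detect this difference in transfer rates". The ICC is taken as 0.1, and significance is judged two-sided at 5%. Four steps, so T = 5 periods, with 18 patients per hospital per period: 5 × 18 = 90 per hospital and 14 × 90 = 1,260. Sequence sizes of 3, 4, 4 and 3 hospitals are read from the crossover columns of Figure 2.

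**2. The plan's own power.** Hussey-Hughes variance for a cross-sectional stepped wedge:

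Var = I·s²(s² + T·τ²) / [(I·U − W)s² + (U² + I·T·U − T·W − I·V)τ²]

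- I = 14 hospitals.
- U (exposed hospital-periods) = 3×4 + 4×3 + 4×2 + 3×1 = 35.
- W (squared column totals) = 3² + 7² + 11² + 14² = 375.
- V (squared row totals) = 3×16 + 4×9 + 4×4 + 3×1 = 103.
- I·U − W = 490 − 375 = 115.
- U² + I·T·U − T·W − I·V = 1,225 + 2,450 − 1,875 − 1,442 = 358.

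Arm-averaged binary variance: (0.25×0.75 + 0.125×0.875)/2 = 0.1484. Then τ² = 0.1 × 0.1484 = 0.01484 and s² = 0.9 × 0.1484/18 = 0.00742. This gives Var = 0.001375, SE = 0.0371, and power = Φ(0.125/0.0371 − 1.96) = 92.1%. With the variance at the control rate, power is 85.1%. The stated figure is reproduced under these standard choices, so the sample size is not the issue here.

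**3. Effect of a capture shift.** Hold true transfers at 25% in both phases. Let intervention months record a share e of extra children, none of them transferred. The observed proportion is 0.25/(1 + e). The chance of a significant result favouring the bundle uses the same design and variance method at the observed rates, with 18 per hospital-period; its nominal value is 2.5%. The documents give no value for e.

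| e (assumed) | Observed proportion | False reduction (points) | Share of 12.5 points | Chance of significance favouring bundle |
|---|---|---|---|---|
| 5% | 0.25/1.05 = 23.8% | 1.2 | 10% | 5% |
| 10% | 0.25/1.10 = 22.7% | 2.3 | 18% | 8% |
| 20% | 0.25/1.20 = 20.8% | 4.2 | 33% | 18% |
| 100% | 0.25/2.00 = 12.5% | 12.5 | 100% | 92% |

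**4. Sensitivity to the assumptions.** No transfers among the added children is the extreme case. If they were transferred at a rate r, the observed proportion would be (0.25 + e·r)/(1 + e). At e = 20% and an assumed r = 12.5%, it is 0.275/1.20 = 22.9%, a false reduction of 2.1 points instead of 4.2. At r = 25% there is no bias. The shift could also run the other way: 10% fewer non-transferred children recorded after crossover gives 0.25/0.90 = 27.8%, which would hide benefit.

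**The case against.** The case against is substantial. Children must be admitted, candidates come from an electronic export, every episode is to be captured with no exclusions, and a common screening log exists. Collection runs through both phases, so no new collector arrives at crossover. Staff and trainers cannot be blinded in an implementation study. The shifts above are assumed, and even 20% accounts for a third of the planned effect. All of this stands, and it limits the room for discretion. It does not close the gap: the export serves to locate patients, and the step from located to included remains a symptom judgement with no fixed rule stated.

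Three stronger readings are tempting, and the documents do not support them.

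- **That the research nurse screens for eligibility.** Section 7.1 is in the passive and names nobody. The nurse's part is an inference from sections 4.2.2, 7.1 and 11.
- **That the trainer sets the denominator.** The export, the intent to capture all episodes and the common log all constrain it.
- **That adherence is audited by the trainer.** Section 7.2 names no auditor. Adherence is measured by deviations from the protocol (7.1, 8.3), and section 12 has the Principal Investigator assess the significance of deviations.

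The protocol is also inconsistent about the role. Section 6.2.2 has a nurse for each site, trained by the lead investigator and study coordinator; section 11 has one HHS nurse, trained by the lead educator. With an HHS-wide nurse and randomisation stratified by HHS (5.1), one person could be collecting from control and intervention hospitals at the same time, which might lessen drift at crossover or might not.

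**Conclusion.** The concern holds in a limited form. Training and data collection belong to one role that cannot be blind to phase, no independent screener is named, and no fixed case-finding rule is stated to apply identically before and after crossover. The outcome at risk is the primary one, and the plausible direction favours the bundle.

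The size cannot be derived from the documents. On the assumed values, 5% to 20% extra capture of children who are never transferred produces a false reduction of 1.2 to 4.2 points and raises the chance of a spuriously favourable result from 2.5% to between 5% and 18%. A reader might infer that the planned effect could be wholly an artefact; that would need the denominator to double, and nothing in the protocol suggests it. The realistic risk is an inflated estimate, or a modest false positive, that the data as collected could not diagnose. The issue belongs to the data collection section of the protocol and is worth correcting because the correction is cheap.

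**What to change.** In section 7.1:

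1. Generate the candidate list centrally, applying one broad, fixed age and respiratory presentation or diagnosis rule to the EDIS and HBCIS exports, identically for every hospital and month. State whether the list counts presentations or admissions, since 3.8.1 and 3.8.3 differ on this.
2. Log every local removal from the list with a reason.
3. Report candidate and included counts by hospital and phase, so that any drift at crossover is visible.
4. Analyse transfers over the full central list, as the primary denominator or at least as a sensitivity analysis specified before database lock.
5. Cross-check transfer status against retrieval and receiving-hospital records. The retrieval services' records should not be the only source: 7.1 collects the mode of transport, and nothing shows that those records cover every transfer.
6. Name the role that screens, and reconcile sections 6.2.2 and 11 on whether the nurse is per site or per HHS and who trains the nurse.

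The cost is protocol wording and a central data pull from systems already in use; the rule can be applied to months already elapsed. There are two downsides. Some mis-coded or ineligible children will enter the list. And because the trained clinicians assign the diagnoses and decide on admission, the rule reduces a shift at crossover without eliminating it, which is why it should be broad.
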